11.3 Determination of sample size

Pathologic complete response is rare following neoadjuvant chemotherapy but was reported in 0-8% of cases³⁹. The current study is designed to test improved rate of pathologic complete response from 10% to 25% treatment with sirolimus followed by durvalumab. Using a MinMax 2-stage design, a total of 31 patients will be enrolled in 2 stages. At the end of stage I, at least 2 of 16 patients must achieve complete pathologic complete response in order for the study to enroll 15 additional patients. The regimen of sirolimus followed by durvalumab will be considered to have sufficient efficacy to warrant further testing in this patient population if 6 or more of the 31 patients achieve a pathologic CR at the end of stage II. The study has 80% power at a 1-sided alpha of 0.1 to show a compelling 25% pCR compared to a less compelling rate of 10%. Because this is a signal finding study, an alpha of 0.1 is considered reasonable since any promising signal will be confirmed in a larger follow-up study.

Planned total number of patients is 31 over 2 years, with an estimated accrual rate of approximately 1-2 patients/month. Racial, ethnic, and gender accrual estimates below are based on 2010 Atlanta Census demographic information.

Accrual Targets			
Ethnic Category	Sex/Gender		
	Females	Males	Total
Hispanic or Latino	1	+ 1	= 2
Not Hispanic or Latino	14	+ 14	= 28
Ethnic Category: Total of all subjects	15 (A1)	+ 15 (B1)	= 30 (C1)
Racial Category			
American Indian or Alaskan Native	0	+ 0	= 0
Asian	1	+ 1	= 2
Black or African American	6	+ 6	= 12

Clinical Study Protocol

Investigational Drug Substance: MEDI4736 Sirolimus (Rapamune)

Study Number **19-20015**

Edition Number: 4

Date: **11 February 2022**

Native Hawaiian or other Pacific Islander	1	+	1	=	2
White	7	+	7	=	14
Racial Category: Total of all subjects	15	(A2)	15	(B2)	30 (C2)
(A1 = A2)		(B1 = B2)		(C1 = C2)	

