3. STUDY DESIGN

3.1 Overview of study design

This is a Phase Ib open-label, single-arm study in newly diagnosed stage I-IIIA NSCLC patients, to test sirolimus in combination with durvalumab as neoadjuvant treatment prior to curative-intent surgical resection. The safety and tolerability as well as efficacy of combination sirolimus with durvalumab will be evaluated in this treatment setting. The study is also designed to investigate a number of laboratory correlative studies to define mechanisms of anti-tumor activity of sirolimus + durvalumab and several potential predictive biomarkers, which will help identify patients who are more likely to respond to treatment. Finally, the study will also include DFS and OS as secondary endpoints.

Up to 31 patients with NSCLC will be enrolled in this study at Emory University Winship Cancer Institute and affiliated sites. Enrollment will occur in 2 parts based on Simon 2 stage design, in which at least 2 of the first 16 patients must achieve pathologic complete response in order for the study to enroll 15 additional patients.

Eligible patients will complete 2 cycles of outpatient study treatment prior to proceeding to standard of care surgical resection. In order to allow a reliable assessment of the contribution of sirolimus versus durvalumab to the observed clinical and PD outcome, treatment will start with sirolimus 6mg orally for one loading dose followed by 2mg orally once daily three weeks prior to the start of durvalumab. Durvalumab will be administered at a dose of 1500mg Q 3 weeks starting on C1D1 for up to 2 cycles that are 21 days in length. Pharmacodynamic analysis will be done using PD samples collected at baseline (tissue) and with blood samples on day -7, C1D1 prior to durvalumab, C1D8, C2D1, C2D8 and at the time of surgery (blood and tissue). Additional post surgery blood samples will be collected at 1, 3, and 6 months post-surgery. See **study schedule of assessments** for schedule of Biomarker collection. Patients will proceed to surgery within a 4-week period post 2nd dose of durvalumab but not earlier than one week after the administration of durvalumab i.e. not earlier than C2D8. Additionally, patients will self-administer heavy water (D2O) 50ml orally three times a day from C1D1 through C1D5 followed by 50ml orally twice a day through the day prior to surgery in order to label dividing cells for research tracking purposes.

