4.4 Replacement of patients

Patients who withdraw consent prior to administration of durvalumab will be replaced. Patients who discontinue study treatment prematurely will not be replaced.

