11.1.2 Efficacy analysis set

The primary and secondary efficacy analyses will include all enrolled patients who have received at least one dose of durvalumab, underwent resection and who do not have EGFR mutant tumors (efficacy population).

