11.2.2 Efficacy analyses

Primary Efficacy Endpoint

The effectiveness of sirolimus followed by durvalumab will be assessed by complete pathologic response rate in the efficacy population. If the null hypothesis is rejected then this is evidence that the response rate exceeds 10% when sirolimus followed by durvalumab is given before resection. The one-sided 95% confidence interval (CI) for complete pathologic response will be reported. Exact binomial test will be used to compare the estimated complete pathologic response rate to the historical reference.

Secondary Efficacy Endpoints

The complete pathologic response rates for PDL-1 negative and PDL-1 positive patients in the *efficacy population* will be presented separately.

A comparison of both the *complete pathologic response* and investigator assessed response rates per RECIST v1.1 rates between the PD-L1 positive and PD-L1 negative groups will be performed by calculating the lower bound of a one-sided 80% CI for the difference, complete pathologic response for PDL-1 positive patients – complete pathologic response for PDL-1 negative patients. Chi-square test or Fisher's exact test will be used to compare the efficacy in term of response rate between the different groups stratified by other factors, respectively. Logistics regression model will be further employed to test the adjusted effect of each other factor on the response rate after adjusting for other clinical factors and demographic factors, respectively. Correlation of response will be performed for tumor mutation burden using spearman correlation coefficient and tested with Wald's test.

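### The stated 80% power holds only if all 31 enrolled patients enter the efficacy population, and the plan makes no allowance for any who do not

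*Combined protocol and SAP*

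**What the plan says.** **Sample size (11.3, repeated in the synopsis).** The null and target pCR rates are 10% and 25%. "Using a MinMax 2-stage design, a total of 31 patients will be enrolled in 2 stages". For stage 1, "at least 2 of 16 patients must achieve complete pathologic complete response in order for the study to enroll 15 additional patients". The final success threshold is 6 pCRs among 31. The power statement is "The study has 80% power at a 1-sided alpha of 0.1 to show a compelling 25% pCR".

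**Analysis population (11.1.2, 11.2.2).** The efficacy set is limited to enrolled patients who "received at least one dose of durvalumab, underwent resection and who do not have EGFR mutant tumors". The primary endpoint "will be assessed by complete pathologic response rate in the efficacy population", and 11.2.2 attaches the 10% reference rate to that endpoint.

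**Enrolment and replacement.** Section 3.1 caps the number: "Up to 31 patients with NSCLC will be enrolled in this study". EGFR mutation is not among the exclusion criteria in 4.2. Sections 4.4 and 6.1 replace only patients who withdraw consent before durvalumab. Section 4.4 adds: "Patients who discontinue study treatment prematurely will not be replaced". Nothing provides for replacing unresected or EGFR-mutant patients.

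**Attrition.** Section 1.6.2 recognises that toxicity may delay or prevent surgery but gives no rate. No EGFR-mutant rate is given either, and no cut-offs are stated for fewer than 16 or 31 evaluable patients.

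**The concern.** The power statement counts enrolled patients, while the primary endpoint counts a subset of them. The two numbers agree only if every enrolled patient is dosed with durvalumab, is resected and has a tumour without an EGFR mutation. Enrolment is capped and replacement is narrow, so the plan has no way to restore a shortfall.

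At stake is how a negative result is read. If patients are lost, a regimen with the target 25% rate would be stopped after stage 1, or judged not worth further testing, more often than the protocol tells its readers.

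**Working it through.** **Inputs from 11.3.** p0 = 0.10, p1 = 0.25, n1 = 16, N = 31, continue if stage 1 pCRs are at least 2, succeed if total pCRs are at least 6, one-sided alpha 0.10.

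**Formula.** With X1 ~ Bin(n1, p) and X2 ~ Bin(N − n1, p):

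P(success) = Σ over x1 ≥ 2 of P(X1 = x1) × P(X2 ≥ 6 − x1)

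**Step 1: reproduce the stated figure (16 + 15, p = 0.25).**

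| Stage 1 pCRs | P(X1) | P(enough in stage 2) | Product |
|---|---|---|---|
| 2 | 0.1336 | 0.5387 | 0.0720 |
| 3 | 0.2079 | 0.7639 | 0.1588 |
| 4 | 0.2252 | 0.9198 | 0.2071 |
| 5 | 0.1802 | 0.9866 | 0.1777 |
| 6 or more | 0.1897 | 1 | 0.1897 |

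The sum is 0.8053, so power is 80.5%. The same formula at p = 0.10 gives a type I error of 0.0788. Both meet the stated 80% and 0.10. A search over two-stage designs confirms that 31 is the smallest total meeting these limits, so the design is minimax as described. The margin over 80% is 0.5 points.

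**Step 2: remove non-evaluable patients.** *Assumptions:* the number lost is illustrative; true pCR is 25% in evaluable patients; cut-offs stay at 2 and 6. The range covers every split of the losses between stages.

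| Evaluable | Splits (stage 1 + stage 2) | Power at 25% | Type I error at 10% |
|---|---|---|---|
| 31 | 16+15 | 80.5% | 7.9% |
| 30 | 15+15 to 16+14 | 77.5-78.3% | 6.8-7.0% |
| 29 | 14+15 to 16+13 | 74.0-75.7% | 5.9-6.1% |
| 28 | 13+15 to 16+12 | 70.0-72.7% | 5.0-5.4% |

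An unresected patient kept in the denominator as a certain non-responder gives the same power as one who is dropped, because cut-offs 2 and 6 must still be reached from the remaining patients.

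**Step 3: false stop at stage 1.** P(X1 ≤ 1) = 0.75^n1 + n1 × 0.25 × 0.75^(n1 − 1).

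- n1 = 16: 0.0100 + 0.0535 = 6.3%
- n1 = 15: 0.0134 + 0.0668 = 8.0%
- n1 = 14: 0.0178 + 0.0832 = 10.1%

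**Step 4: would a lower final cut-off repair it?** With 5 in place of 6, the two-stage type I error is 15.4-15.9% at 30 evaluable, 13.6-14.6% at 29 and about 12-13% at 28. All exceed 0.10, so in this range the cut-off cannot be lowered within the stated alpha.

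**The case against.** The strongest reply is that no printed number is wrong. That stands: 80% is correct for the rule as written, and the point is a missing allowance, not a miscalculation.

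The second reply is that the size rests on assumed losses. This also stands. The documents contain reassuring text: 1.6.2 says that neoadjuvant therapies targeting the PD-1 pathway have not significantly prevented surgery in single-agent studies, and 1.5.1.1 reports that the approach was feasible at this institution. The same section 1.6.2 says that the risks of the combination are unknown. Some loss is plausible, but no particular number is supported. With one loss the shortfall is only 2 to 3 points.

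The third reply is that 11.3 sets both rates beside 31 enrolled patients. If 25% is the rate per enrolled patient, the 80.5% stands. But 11.2.2 places the 10% reference in the efficacy population, and the benchmark and the target it is tested against should refer to the same patients.

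Three stronger readings are tempting, and the documents do not support them:

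- *An excluded patient can never supply a pCR, however patients are counted.* This is true of unresected patients. A resected EGFR-mutant patient could have a pCR, and the threshold in 11.3, read literally, counts pCRs among 31 patients without an EGFR restriction. Sections 11.1.2 and 11.2.2 remove that patient, but nothing in the plan scores the patient as a non-responder.
- *Power collapses with heavier losses, for example to 64% with 26 evaluable (13 + 13).* That figure needs cut-off 6 to be kept. A cut-off of 5 there has a two-stage type I error of 9.8%, within 0.10, and power of 76.8%. The plan names no cut-off below 31, so 64% is not a property of 26 evaluable patients.
- *The trial is in fact underpowered.* That cannot be said without a loss rate.

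**Conclusion.** The concern holds in conditional form. The 80% in 11.3 and the synopsis describes 31 patients who all belong to the efficacy population, and the plan neither states that condition nor protects it. One loss takes power to about 77-78%, two to 74-76% and three to 70-73%. Losing one or two stage 1 patients raises the chance of wrongly stopping a 25% regimen from 6.3% to 8.0% or 10.1%.

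These figures assume a 25% pCR rate in evaluable patients, cut-offs fixed at 2 and 6, and an illustrative number of losses. Type I error is not inflated: it falls as patients are lost. The defect is in what the power statement tells the reader and does not invalidate the two-stage rule.

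**What to change.** Keep 31 patients and both cut-offs. In 11.3 and the synopsis, replace the power sentence with text to this effect:

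*With 31 patients evaluable in the efficacy population (16 in stage 1), the rule has 80.5% power at a pCR rate of 25% and a one-sided type I error of 7.9% at 10%. If the cut-offs stay at 2 and 6 and the true rate in evaluable patients is 25%, power is about 77-78% with 30 evaluable, 74-76% with 29 and 70-73% with 28, depending on the stage at which patients are lost. The probability of stopping at stage 1 is then 6.3%, 8.0% or 10.1% with 16, 15 or 14 evaluable.*

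The change costs no patients and alters no procedure. Its downside is a stated power that looks less favourable.

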12. ETHICAL AND REGULATORY REQUIREMENTS

12.1 Ethical conduct of the study

The study will be performed in accordance with ethical principles that have their origin in the Declaration of Helsinki and are consistent with ICH/Good Clinical Practice, and applicable regulatory requirements Patient data protection.

12.2 Ethics and regulatory review

This protocol, the Informed Consent Forms, any information to be given to the patient, and relevant supporting information must be submitted to the Emory IRB by the Principal Investigator and reviewed and approved by the Emory IRB before the study is initiated.

The Principal Investigator is responsible for providing written summaries of the status of the study to the IRB annually or more frequently in accordance with the requirements, policies, and procedures established by the IRB. Investigators are also responsible for promptly informing the IRB of any protocol amendments.

In addition to the requirements for reporting all adverse events to the Sponsor, investigators must comply with requirements for reporting serious adverse events to the local health authority and IRB. Investigators may receive written IND safety reports or other safety-related communications from the Sponsor.

12.3 Informed consent and confidentiality

Patient medical information obtained by this study is confidential and may be disclosed to third parties only as permitted by the Informed Consent Form (or separate authorization for use and

Clinical Study Protocol

Investigational Drug Substance: MEDI4736 Sirolimus (Rapamune)

Study Number **19-20015**

Edition Number: 4

Date: **11 February 2022**

disclosure of personal health information) signed by the patient, unless permitted or required by law.

The Sponsor maintains confidentiality standards by coding each patient enrolled in the study through assignment of a unique patient identification number. This means that patient names are not included in data sets that are transmitted to any Sponsor location.

Medical information may be given to a patient's personal physician or other appropriate medical personnel responsible for the patient's welfare, for treatment purposes.

Given the complexity and exploratory nature of the analyses, data derived from exploratory biomarker specimens will generally not be provided to study investigators or patients unless required by law. The aggregate results of any conducted research will be available in accordance with the effective Sponsor policy on study data publication

12.4 Changes to the protocol and informed consent form

Any change or addition (excluding administrative) to this protocol requires a written protocol amendment that must be reviewed by the sponsor and the investigator before implementation. Amendments significantly affecting the safety of subjects, the scope of the investigation or the scientific quality of the study require additional approval by the IRB at Emory. A copy of the written approval of the IRB must be provided to AstraZeneca. Examples of amendments requiring such approval are:

1. increases in drug dose or duration of exposure of subjects,
2. significant changes in the study design (e.g. addition or deletion of a control group),
3. increases in the number of invasive procedures,
4. addition or deletions of a test procedure required for monitoring of safety.

These requirements for approval should in no way prevent any immediate action from being taken by the investigator or by AstraZeneca in the interests of preserving the safety of all patients included in the trial. If an immediate change to the protocol is felt to be necessary by the investigator and is implemented for safety reasons AstraZeneca must be notified and the IRB at the center must be informed immediately. Amendments affecting only administrative aspects of the study do not require formal protocol amendments or IRB approval but the IRB must be kept informed of such administrative changes. Examples of administrative changes not requiring formal protocol amendments and IRB approval include:

1. changes in the staff used to monitor trials
2. minor changes in the packaging or labeling of study drug.

12.5 Audits and inspections

The Data and Safety Monitoring Committee (DSMC) of the Winship Cancer Institute will provide oversight for the conduct of this study. The DSMC functions independently within Winship Cancer Institute to conduct internal monitoring functions to ensure that research being conducted by Winship Cancer Institute Investigators produces high-quality scientific data in a manner consistent with good clinical practice (GCP) and appropriate regulations that govern clinical research. Depending on the risk level of the protocol, the DSMC review may occur every 6 months or annually. For studies deemed High Risk, initial study monitoring will occur within 6 months from the date of the first subject accrued, with 2 of the first 5 subjects being reviewed. For studies deemed Moderate Risk, initial study monitoring will occur within 1 year from the date of the first subject accrued, with 2 of the first 5 subjects being reviewed. Subsequent monitoring will occur in routine intervals per the Winship Data and Safety Monitoring Plan (DSMP).

The DSMC will review pertinent aspects of the study to assess subject safety, compliance with the protocol, data collection, and risk-benefit ratio. Specifically, the Winship Cancer Institute Internal Monitors assigned to the DSMC may verify informed consent, eligibility, data entry, accuracy and availability of source documents, AEs/SAEs, and essential regulatory documents. Following the monitoring review, monitors will provide a preliminary report of monitoring findings to the PI and other pertinent individuals involved in the conduct of the study. The PI is required to address and respond to all the deficiencies noted in the preliminary report. Prior to the completion of the final summary report, monitors will discuss the preliminary report responses with the PI and other team members (when appropriate). A final monitoring summary report will then be prepared by the monitor. Final DSMC review will include the final monitoring summary report with corresponding PI response, submitted CAPA (when applicable), PI Summary statement, and available aggregate toxicity and safety data.

The DSMC will render a recommendation and rating based on the overall trial conduct. The PI is responsible for ensuring that instances of egregious data insufficiencies are reported to the IRB. Continuing Review submissions will include the DSMC recommendation letter. Should any revisions be made to the protocol-specific monitoring plan after initial DSMC approval, the PI will be responsible for notifying the DSMC of such changes. The Committee reserves the right to conduct additional audits if necessary.

Clinical Study Protocol

Investigational Drug Substance: MEDI4736 Sirolimus (Rapamune)

Study Number **19-20015**

Edition Number: **4**

Date: **11 February 2022**

13. STUDY MANAGEMENT

13.1 Training of study site personnel

Each of the Emory University Affiliated Study sites will undergo training sessions for the sub-investigators and the clinical study staff, utilizing a standardized PowerPoint presentation that will highlight pertinent details of the protocol.

13.2 Monitoring of the study

13.2.1 Source data

Source data will be logged onto Oncore per Winship Standard procedures.

13.3 Study timetable and end of study

The end of this study is defined as Last Patient Last Visit, which is expected to be when the last patient completes the survival follow-up (which may occur in person or by phone). This is expected to occur approximately 2 years after the last patient receives the last dose of neoadjuvant durvalumab. The treatment period of this study will end when the last data point required for primary efficacy analysis (i.e., pathology evaluation at time of surgery) is obtained. This is expected to occur approximately 30 days after the last patient's surgery.

After completing treatment with sirolimus + durvalumab, patients will be followed for survival for up to 2 years after the last patient receives the last dose of durvalumab (by phone or in person). Patients removed from study for unacceptable adverse event(s) will be followed until resolution or stabilization of the adverse event. The recruitment period is expected to last 1.5 to 2 years. The total length of the study, from screening of the first patient to the end of the study, is expected to be approximately 4 years.

14. DATA MANAGEMENT

Data will be collected using an institutional electronic data recording system, Oncore. Electronic case report forms and study calendar will be generated prior to study activation. Investigator responsibilities are set out in the ICH guideline for Good Clinical Practice (GCP) and in the US Code of Federal Regulations. The Investigator will permit study-related audits by AstraZeneca or its representatives, IRB/EC review, and regulatory inspection(s) (e.g., FDA, EMEA), providing direct access to the facilities where the study took place, to source documents, to CRFs, and to all other study documents.

Clinical Study Protocol

Investigational Drug Substance: MEDI4736 Sirolimus (Rapamune)

Study Number **19-20015**

Edition Number: 4

Date: **11 February 2022**

The Investigator, or a designated member of the Investigator's staff, must be available at some time during audits to review data and resolve any queries and to allow direct access to the subject's records (e.g., medical records, office charts, hospital charts, and study related charts) for source data verification. The data collection must be completed prior to each visit and be made available so that the accuracy and completeness may be checked.

The Investigator must ensure that the records and documents pertaining to the conduct of the study and the distribution of the protocol therapy, that is copies of CRFs and source documents (original documents, data, and records [e.g., hospital records; clinical and office charts; laboratory notes; memoranda; subject's diaries or evaluation checklists; SAE reports, pharmacy dispensing records; recorded data from automated instruments; copies or transcriptions certified after verification as being accurate copies; microfiches; photographic negatives, microfilm, or magnetic media; x-rays; subject files; and records kept at the pharmacy, at the laboratories, and at medico-technical departments involved in the clinical study; documents regarding subject treatment and drug accountability; original signed informed consents, etc.]) be retained by the Investigator for as long as needed to comply with national and international regulations (generally 2 years after discontinuing clinical development or after the last marketing approval).

